5.2 Number of Participants

A total of 120 YMSM participants will be enrolled in Aim 2 of study ($n = 60$ per condition). Assigning 60 participants to each condition (iCBT vs. self-monitoring) and accounting for 20% attrition, a liberal estimate based on our previous online RCTs (i.e., 93-100%), will provide $\geq 80\%$ chance of detecting a difference ($p < .05$) between the conditions of $d = .40$, which is significantly lower than what we found when comparing in-person ESTEEM to waitlist ($d = .59$ for CAS, $d = .55$ for depression) and lower than even the smallest average meta-analytic effect ($d = .66$) of iCBT compared to weak control conditions for depression. For Aim 3, a total of 55 participants, including ($n = 20$) Aim 2 participants, ($n = 6$) study therapists and supervisors, ($n = 8$) government administrators and leadership, ($n = 7$) LGBTQ community organization staff, and ($n = 7$) medical providers will be interviewed in order to identify themes in regard to barriers and facilitators of implementing iCBT ESTEEM among Chinese YMSM.

5.3 Eligibility Criteria

In order to be eligible for inclusion in Aim 2 of the study, an individual must meet all of the following criteria:

- 16-30 years old
- Live in Hunan province China
- Current gender identity as male
- Report past 12-month sex with men
- Be confirmed HIV-negative upon at-home testing
- Report past 3-month condomless/PrEP-less anal sex

- Past-week symptoms of depression or anxiety using the Brief Symptom Inventory-4 cutoff of 2.5 on either the depression subscale, anxiety subscale, or both
- No past 3-month mental health services of more than 2 visits per month
- Weekly access to internet on a laptop, desktop, or tablet device
- Ability to read, write, and speak in Mandarin
- Provision of informed consent

Any individual who meets any of the following criteria will be excluded from participation in this study:

- Current active suicidality or homicidality (defined as active intent or concrete plan, as opposed to passive ideation)
- Evidence of active and untreated mania or psychosis that could interfere with the participant's ability to volitionally consent to research or interfere with their ability to safely and reliably complete research

5.4 Recruitment Procedures

Recruitment strategy: For both the full RCT and pilot study, we will recruit YMSM via advertisements on YMSM's social networking platforms (e.g., QQ, WeChat, Blued) and the lobbies of Zuo An Cai Hong (Cai Hong = "rainbow"), an SGM-friendly community-based organization with 7 offices in 7 cities of Hunan province that provides ~11,000 HIV tests/year and free counseling to YMSM and has a strong collaboration with the Chinese CDC Hunan office.

We will create online and paper (e.g., posters, flyers; see attached recruitment flyers on IRES) advertisements for this study to post widely on the above virtual and physical sites. Based on prior experience, we have allocated substantial recruitment funds to cover the cost of recruitment materials and outreach (e.g., in the unforeseen circumstance that QQ begins charging researchers to post recruitment ads).

The CSU team has a graduate student under [name] supervision who will serve in the role as a full-time recruiter. This individual, along with [name], has deep social connections with the YMSM community and is familiar with existing and emerging virtual and physical sites where YMSM socialize. They also possess knowledge of means to reach YMSM who might not be out (e.g., via virtual and physical cruising grounds), who therefore might be particularly suitable for our minority-stress-focused intervention.

Comprehension test: Before we randomize participants into the full trial, we will conduct a comprehension test the ESTEEM iCBT treatment with 10 YMSM to ensure their comprehension of the module material, as well as glean their feedback on the usability of the iCBT online platform. Our two pilots for this proposal (i.e., cultural adaptation in China + iCBT usability testing in the US) have already led to the creation of the in-person delivery materials for Chinese ESTEEM (e.g., manual, participant handouts) and established the technical feasibility of our iCBT platform. As such, the Chinese-adapted materials (e.g., manual, handouts) are ready to be transformed into iCBT content (e.g., self-guided exercises, videos, counselor instructions). Given the previous efficacy testing of in-person Chinese ESTEEM and iCBT in our US study, comprehension testing will occur over the course of 2 weeks with a focus on 10 YMSM reviewing the online treatment material, receiving counselor feedback, and providing feedback on the materials via answering brief questions after each module on its usability. For this comprehension test, the only inclusion criteria will be:

- 16-30 years old
- Live in Hunan province China
- Current gender identity as male

- Report past 12-month sex with men
- Weekly access to internet on a laptop, desktop, or tablet device
- Ability to read, write, and speak in Mandarin
- Provision of informed consent

These 10 YMSM for the comprehension test will not complete the study measures, with the exception of the 30-day Timeline Follow-Back assessment at the end of the pilot in order to test the usability of this assessment on the Sojump platform. After review of the ESTEEM iCBT materials, participants will provide feedback to the CSU research team on their comprehension of the materials, as well as respond to questions from a qualitative interview conducted by the CSU research team about their experience.

Evidence for successful attainment of recruitment goals: While recruiting 120 participants within a 10-month timespan is ambitious, we have easily exceeded this recruitment goal in equally high-stigma regions of much smaller population size. For instance, in our trial of a brief online intervention for sexual minorities in rural Appalachia, an area also with high stigma, we recruited 108 participants in 8 months, despite the six Appalachian counties of our geographic recruitment zone having 0.5M inhabitants (IRB #1512016952). By contrast, Hunan province, characterized by equally high stigma toward YMSM, has a population of nearly 70M (140 times more inhabitants than live in our Appalachia recruitment zone). [name] has used the strategies proposed in this study (e.g., passive and active recruitment, leveraging her deep connections with YMSM-friendly community organizations) to previously enroll 80 MSM across 9 months into a multi-session motivational interviewing intervention. Finally, [name] has shown through his research with YMSM in Romania that he can meet this recruitment goal. In his current NIMH RCT in Romania, the research team has enrolled 60 YMSM over the first 6 months. This matches the rate at which he has recruited YMSM into his US-based RCTs, which have achieved sample sizes of 250 YMSM in approximately 25 months.

Retention: We have refined our retention strategies across several previous studies with YMSM in China, low-and-middle income countries, and in high-stigma regions of the US. First, to retain participants across the study, we will use all communication permitted by participants, including a study WeChat account, and frequent reminders. Second, to ensure high engagement with the iCBT sessions, we have built-in lessons-learned from our US-based usability test. For instance, we now include an introductory phone call between the counselor and participant. Also, one of our videos – shown at the start of the intervention – includes a brief “how-to” demonstration that shows participants how to navigate the iCBT platform itself. Third, we include reasonable financial incentives in Chinese currency (i.e., Renminbi; RMB) to compensate participants for their time spent on study-related tasks, amounting to 50RMB per iCBT session (for those in the iCBT ESTEEM condition), 30RMB for each weekly self-monitoring survey (for those in the self-monitoring condition), and 150RMB per assessment (baseline, 4-month follow-up, 8-month follow-up).

We have used these retention strategies previously to attain very high retention in our online RCTs. [name] attained 100% retention with 77 YMSM in his first online RCT. [name] also retained 88% of participants at follow-up in an online HIV-prevention RCT in Romania. Using near-identical strategies as will be used here, [name] retained 83% of YMSM in her in-person motivational interviewing-based HIV-prevention RCT in Hunan. We estimate that we will retain at least 80% of participants, a quite liberal goal given that we have exceeded this goal in our previous studies with YMSM in high-stigma contexts. Nonetheless, our study is powered with even 20% attrition, to detect effects smaller than those found for identical outcomes (e.g., condomless anal sex, depression) in our previous RCTs with YMSM.

Qualitative Interviews: For the interviews conducted with LGBTQ organization staff, government administrators and leadership, and medical providers, the PI at CSU and her research team will contact the governmental and NGO professionals in their network about participating in these interviews. All participants will be compensated 200 RMB (\$31.48) for their participation in interviews.

5.5 Consent/Accent Procedures/HIPAA Authorization

Comprehension test. A waiver of documentation of consent is planned for the all portions of this comprehension test study (see attachments on IRES for the online screener). For the comprehension test, potential participants will take the online screener for the study via the secure CSU Sojump survey software. As previously noted, the only inclusion criteria for the comprehension test will be: 16-30 years old, live in Hunan province China, current gender identity as male, report past 12-month sex with men, weekly access to internet on a laptop, desktop, or tablet device, ability to read, write, and speak in Mandarin, and provision of informed consent (see Section 5.3 for inclusion criteria for the full study). An RA at CSU will schedule a WeChat call with 10 YMSM participants who express interest in participating in the comprehension test. Prior to the WeChat call, the CSU RA will send a copy of the consent form via WeChat to the participant and ask them to review the form before the WeChat call. During the WeChat call, the CSU RA will read through the consent form and answer any questions from the participants. Participants will be informed on the consent form that they will receive 200RMB for reviewing the 10 iCBT session modules and 50RMB for participating in a follow-up interview. Any ineligible participants will be informed at the end of the online screener of their ineligibility for the study.

RCT. For the full RCT study (Aim 2), consent will be obtained at three time points. A waiver of documentation of consent is planned for all portions of this study:

First, participants will complete an initial online screener via the secure CSU Sojump survey software (see attachments on IRES for the online screener).

Second, if participants are eligible for the study based on the online screen, a CSU RA will schedule a video screen via WeChat for further assessment. At the beginning of this video call, participants will provide verbal consent before continuing with the video screen (see the Measure Packet uploaded on IRES for the script that will be followed for the video screener). Ineligible participants will be informed at the end of the video screener of their ineligibility for the study. If participants are eligible following the video screener, an at home HIV/STI testing kit will be sent to the participant via mail within 2 days of the video screener.

Third, a CSU RA will send participants who screen negative based on the at-home HIV testing a copy of the consent form via WeChat. A WeChat call will then be scheduled with each participant to review the consent form and assess whether participants understand the information in the consent form. As such, a waiver of signed documentation of consent is planned for the full RCT study (see attachments on IRES for the full RCT consent form).

Participants will be informed on the consent form that they will receive 50RMB per iCBT session (for those in the iCBT ESTEEM condition), 30RMB for each weekly self-monitoring survey (for those in the self-monitoring condition), and 150RMB per assessment (baseline, 4-month follow-up, 8-month follow-up).

Participants will be provided with the PI's contact information at CSU and directed to call or email the PI if they have any questions or concerns. The PI at CSU, [name], will be responsible for ensuring that online consent has been obtained.

Waiver of Parental Consent for Participants Ages 16-17. Involving Chinese adolescent YMSM in research to develop interventions for reducing depression, anxiety, and suicidality is essential for addressing the substantial mental health disparities affecting this population. Sexual orientation disparities in depression, anxiety, and suicidality are well-documented among Chinese adolescent YMSM (Huang et al., 2018; Zhang, Wong, Ip, Fan, & Yip, 2017); however, no evidence-based intervention has been developed to address the unique stressors faced by Chinese adolescent YMSM to reduce their disproportionate burden of mental health problems. To develop an intervention tailored to the needs of this population, our research involvement.

As such, the present study proposes to waive parental consent for adolescents ages 16-17 in the Hunan province of China for this study. Several reasons are presented in support of waiving parental consent. First, waiving parental consent would not adversely affect the rights and welfare of the participants and, in fact, obtaining parental consent would be impractical for many participants and potentially increase risk given the stigma toward sexual minorities in China. Parental rejection of one's sexual orientation is a robust risk factors for resultant depression, anxiety, and suicidality (Puckett et al., 2015; Ryan et al., 2010). Requiring parental consent and, thus, concurrent disclosure of sexual minority identity, increases the risk of such rejection. In some cases, parental consent can also hinder sexual minority participants' willingness to participate in research (e.g., Fisher, Fried, Puri, Macapagal, & Mustanski, 2018; Flores, McKinney, Arscott, & Barroso, 2018; Macapagal, Coventry, Arbeit, Fisher, & Mustanski, 2017; Taylor, 2018). For these reasons, parental consent for this study is not a reasonable ethical requirement to protect sexual minority adolescents in those states that do not require parental consent for adolescents ages 16-17 to receive mental health treatment.

Second, based on previous research (Melton, 1983; Susman, Dorn, & Fletcher, 1992; Weithorn, 1994), adolescents are fully capable of not only providing informed consent in situations in which parental consent poses significant risks, but are also as capable as adults of the decision-making capacity to provide informed consent.

Third, throughout the multiple points of consent, research staff at CSU will provide substitutes for parental consent to protect all study participants, including those ages 16-17. These protections include those listed in our current IRB-approved protocol for this study, including: (1) reviewing all participant survey responses and therapy-related exercises for indications of suicidality and severe distress by a member of the CSU's clinical team; (2) responding quickly to such distress by encouraging access to a 24/7 crisis hotline (see clinical protocol for more details); and, (3) contacting participants who indicate distress by our own clinical staff within one business day. The Clinical Protocol, successfully employed in our other studies of this treatment and its components when delivered both in-person and online, continues to guide the protection of study participants.

Lastly, as described in Section 7.3 and throughout this protocol, the present study poses minimal risk. As previously described, Chinese adolescent YMSM present at greater risk for depression, anxiety, and suicidality compared to their heterosexual peers (Huang et al., 2018; Zhang et al., 2017). The research procedures of the present study are not expected to increase this risk, but instead are intended to decrease it, as demonstrated in our pilot studies of this treatment and its components delivered both in person and online to young adults ages 18 to 35 (e.g., [name], Hatzenbuehler et al., 2015; [name], Williams et al., 2019). Indeed, participation in our previous similar intervention studies, including an in-person pilot study of the same intervention in China, reduced participants' average risk of depression and suicidality from baseline levels. The research procedures of the present study involve completing sexual and mental health questionnaires, reading written materials about mental health and stress, and engaging in asynchronous (i.e., not live) communication

with a study counselor about mental health and stress. These procedures do not pose greater risk than those encountered in daily life (e.g., taking a health education class) or other activities not requiring parental consent for sexual minority adolescents (e.g., attending a community LGBTQ meeting).

Qualitative Interviews: For the qualitative interviews (Aim 3), all RCT participants will already have completed eligibility screening and associated consent procedures. Thus, participants will provide additional consent for the interview at the time of the interview. The interviewer and participant will together review a consent form together that details interview risks/benefits and precautions against risk. Once participants have demonstrated that they fully understood the consent, they will be asked to provide verbal consent as well as sign an interview consent form using the Sojumpr survey platform (see attached in IRES). We foresee minimal risk for the potential of emotional distress as a result of the interview. If participants do not feel comfortable/experience distress answering specific questions, they will be informed that they may refrain from answering any question. Nonetheless, in the event of disclosure of emotional distress, the same procedures will be followed as in Aim 2. Interviews with community stakeholders are unlikely to pose risks given these individuals' professional involvement with LGBTQ-related stressors and therapies on a regular basis.

References (for Section 5.5)

Fisher, C. B., Fried, A. L., Puri, L. I., Macapagal, K., & Mustanski, B. (2018). "Free Testing and PrEP without outing myself to parents:" Motivation to participate in oral and injectable PrEP clinical trials among adolescent men who have sex with men. *PLoS one*, 13(7), e0200560.

Melton, G. B. (1983). Toward "personhood" for adolescents. Autonomy and privacy as values in public policy. *American Psychologist*, 38, 99 –103.

6.1 Study Procedures

We propose to test the efficacy of an online CBT intervention (ESTEEM iCBT) among 120 Chinese YMSM. The proposed prospective study will follow a 2-arm RCT design where participants will be randomized into either the ESTEEM iCBT treatment group or self-monitoring control group (both conditions described in further detail in Section 4, Study Design).

For the comprehension test, 10 YMSM will be recruited to review the ESTEEM iCBT treatment materials in order to assess their comprehension of the online treatment materials, as well as glean feedback in regard to usability of the iCBT online platform. In contrast to the full RCT, the only inclusion criteria for this comprehension test will be:

- 16-30 years old
- Live in Hunan province China
- Current gender identity as male
- Report past 12-month sex with men
- Weekly access to internet on a laptop, desktop, or tablet device
- Ability to read, write, and speak in Mandarin
- Provision of informed consent

Additionally, these participants will not complete baseline surveys as will be conducted for the full RCT. Also, since the purpose of the pilot is to ensure comprehension of the treatment material, participants will be asked to complete the 10 modules of the treatment over the course of 2 weeks. These 10 YMSM participants will be asked to share their feedback about their experience with the online CBT intervention via a WeChat call with a CSU research team member at the end of their participation.

For the full RCT study, 120 YMSM will be recruited via strategies and based on eligibility criteria described in Sections 5.4 and 5.3, respectively. Participants will first complete an online screener on the secure Sojump survey platform. If eligible, participants will be directed

to a separate Sojump survey where they will be asked to provide their contact information in order to be contacted for participation in the study. For participants who provide contact information, RAs at CSU will contact participants via their preferred contact method and ask to schedule a video screener on WeChat. Upon completion and deemed eligible from the video screener, participants will be mailed an at home HIV/STI testing kit. The estimated time of arrival based on the mailing system in Hunan province is 1-2 days. The RA at CSU will be able to check the mailing status of the testing kit. A CSU research team member will contact participants on WeChat after 5 business days of sending the HIV/STI testing kit if the participant has not sent the CSU team their results.

The kit will consist of a self-HIV testing kit using Alere Determine HIV 1/2 rapid assay (Alere Medical Co., Japan), a type of finger-prick-based HIV testing kit, approved by China's State Food and Drug Administration and the US Food and Drug Administration (sensitivity: 100.00%; specificity: 99.68%) on all participants. The same counseling and testing clinical protocol will be followed for syphilis testing, which will utilize the Treponema pallidum antibodies rapid test (emulsion process) (Abon biomedicine co., Hangzhou), a type of blood-based testing kit to detect syphilis (sensitivity: 99.01%, specificity: 99.35%). Participants will self-administer these sample collections following instructions that will be provided via QR code that will be enclosed in their kits.

Appropriate risk-reduction counseling will be provided to all participants on the same day of testing. Enclosed within testing kits, all participants will receive lubricant and condoms. The rapid test results for both HIV and syphilis will be ready to be read by participants in 20 minutes. HIV/STI test results will be discussed with participants by study counselors. Like conventional HIV enzyme immunoassays (EIAs), rapid HIV/STI tests are screening (i.e., not diagnostic) tests that require diagnostic confirmation by Western Blots if reactive (positive). Participants who test preliminarily positive (or have inconclusive tests) will be immediately linked to Zuo An Cai Hong for confirmatory testing, care, and treatment. Counselors will offer to make an appointment for participants at a local Zuo An Cai Hong, which has 7 offices across Hunan province. Participants testing HIV positive will not be randomized into the study, as HIV negative status is one of the inclusion criteria, so they will receive immediate HIV/STI counseling by one of our counselors, followed by medical attention by Zuo An Cai Hong to which they will be promptly linked. Participants who test negative will be given the option of continuing to move forward with the research study.

Participants who continue to express interest in the study will be sent a copy of the consent form via WeChat. Participants will be asked to read the consent form on their own. CSU RAs will schedule a consent call with participants via WeChat to read over the consent form with them, as well as check their understanding of the consent form via asking questions about the content of the study and ability for participants to withdraw from the study at any time. After participants provide verbal consent, we will assign them a username and password for the Karolinska Institutet's secure iCBT online platform that houses the ESTEEM iCBT treatment and self-monitoring weekly assessment for both conditions. Participants will be required to login to the Karolinska Institutet's secure iCBT platform before they are sent the baseline assessments. Upon signing into the iCBT online platform, a CSU RA will send a hyperlink to the participant via WeChat to complete the baseline surveys on Sojump. After completion of the baseline completion, a CSU RA will schedule a final WeChat call with each participant for their randomization into either the ESTEEM iCBT or self-monitoring condition.

For participants assigned to ESTEEM iCBT, they will be assigned a study therapist and will be contacted by their therapist to schedule a 30-minute introductory call via WeChat. During this conversation, therapists will explain the structure of the study and briefly discuss the participant's motivations and goals for participating in the study. All participants will then complete one session (i.e., ESTEEM iCBT or self-monitoring) per week. If participants miss

a session, as determined by daily therapist and RA review of session access and self-monitoring or homework completion, they will receive a reminder via a WeChat message to complete the session. Participants will also be asked to schedule a check-in WeChat call with their study therapist two-weeks post-randomization to discuss their progress through the study sessions. Participants will have a window period of four months (i.e., 17 weeks) to complete all 10 sessions.

Lastly, all participants will be sent messages on WeChat to complete 4-month and 8-month follow-up assessments. For all assessment time points, automatically generated alerts from Sojump will be sent to CSU study staff in response to any participants who indicate suicidality in response to suicidality assessments, at which point a clinical staff member part of the CSU team will implement the clinical protocol. For the 8-month follow-up, a second at-home HIV/STI testing kit will be mailed to participants. The same procedure as described above will be followed in regard to participants administering this test and reporting results to CSU study counselors for follow-up.

See Table 1 in Section 11.1 for a Visit Schedule Table with study procedures listing all points of data collection.

For Aim 3 qualitative interviews, a proportion of participants will be contacted following completion of their 8-month follow-up window to schedule the interview using their preferred method of contact. During the interview, the interviewer will ask about participants' experience with the study, its online format, and its perceived efficacy (see IRES for attached interview guide). Community stakeholders will be contacted over email by the PI at CSU, [name], to participate in focus group discussions with other participants of similar professions/roles. Community stakeholder participants will be shown a brief presentation on the format and content of the treatment intervention, as well as preliminary findings. These participants will then be asked about barriers and facilitators to implementation (see IRES for attached interview guide).

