
Flow Diagram for the 2-Arm RCT China ESTEEM iCBT Design

Aim 3 of the study will identify barriers and facilitators for uptake and scale of Chinese ESTEEM iCBT within existing public and non-governmental organizations (NGO) settings. We will first review Aim 2 data for YMSM completion metrics (# sessions completed, points of drop-off) and moderators of intervention efficacy (as described below). Next, we will interview a subset of Aim 2 participants ($n=20$) as well as counselors and therapy supervisors ($n=6$) for their impressions of the acceptability of Chinese ESTEEM iCBT and needed improvements before implementation. We will also interview ($n = 8$) government administrators and leadership, ($n=7$) LGBTQ community organization staff, and ($n = 7$) medical providers who have expressed interest in online interventions for YMSM and who can ultimately implement this intervention, if efficacious.

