4.1 Study Duration

The entire study, including data analysis, is expected to last until May 2023. Participation for the 10 YMSM in pilot testing will begin by January 2021. Participation for the full study RCT will begin by October 2021. The final 8-month follow-up assessments are anticipated to end by November 2022. Participation for the qualitative interviews will begin by June 2022 (upon final survey completion of the first RCT participants). Data analysis is expected to occur beginning in December 2022 until May 2023.

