9.6 Study Completion

Data collection for the study will end by November 30, 2022. Data analysis is expected to occur from December 2022 to May 2023. The study is anticipated to be completed by June 1, 2023.

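### Aim 3 calls for a review of efficacy moderators before interviews that start by June 2022, while 8-month follow-up is still open and analysis begins only in December 2022

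*Protocol*

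**What the plan says.** **Order of steps.** The Aim 3 paragraph stands in the Synopsis (Study Design) and again in Protocol Section 4. It says: "We will first review Aim 2 data for YMSM completion metrics (# sessions completed, points of drop-off) and moderators of intervention efficacy". Interviews with trial participants, counselors and supervisors come next, together with interviews of government, LGBTQ-organization and medical staff.

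**What the review involves.** Protocol 7.2.1 defines the moderator analysis as the outcome mixed models with moderator-by-arm interactions added. SAP 8.4.3.1 uses a condition-by-time-by-moderator model with both the 4-month and the 8-month endpoints.

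**Calendar.** Protocol 4.1 gives four dates:
- "Participation for the full study RCT will begin by October 2021"
- "Participation for the qualitative interviews will begin by June 2022 (upon final survey completion of the first RCT participants"
- "The final 8-month follow-up assessments are anticipated to end by November 2022"
- "Data analysis is expected to occur beginning in December 2022 until May 2023"

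Protocol 9.6 adds: "Data collection for the study will end by November 30, 2022".

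**Stakeholder sessions.** Protocol 6.1: "Community stakeholder participants will be shown a brief presentation on the format and content of the treatment intervention, as well as preliminary findings". The questions on barriers and facilitators follow that presentation.

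**Access to results.** Protocol 7.2.3 gives the DSMB risk-related data by condition, and Section 8.7 makes confidentiality one of the DSMB's duties. SAP 7.1 lists efficacy and futility among the monitoring topics, without a look time, a boundary or an access rule. Neither document says who else may see outcomes by arm before follow-up ends.

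**The concern.** A moderator of efficacy cannot be examined without outcomes split by arm. If that review really precedes the interviews, and the interviews really open in June 2022, the team must compare the arms months before the stated start of analysis and while the primary endpoint is still being collected.

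Two things would be at stake. First, the primary outcome is self-reported condomless anal sex. The CSU team holds the randomization call, sends the follow-up survey messages and discusses home-test results, and its principal investigator invites the stakeholders. Early knowledge of which arm is ahead could colour contact with participants still due for their 8-month survey, and so affect reporting or retention. Second, implementation interviews shaped by early efficacy or moderator signals would rest on unstable estimates that may differ from the final ones.

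**Working it through.** **Inputs.** RCT start, interview start, end of follow-up and analysis start: Protocol 4.1. End of data collection: Protocol 9.6. Sample size 120: Protocol 7.1. Assumed, not stated: start on 1 October 2021, uniform accrual, no dropout.

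**Step 1: reproduce the plan's own date.** October 2021 + 8 months = June 2022 (1 June for a start on 1 October, 30 June for a start on 31 October). This matches the stated interview start, which is tied to the first participants' last survey.

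**Step 2: gap to analysis.** June to December 2022 is about 6 months. A moderator review on complete 8-month data within the stated analysis period cannot begin before December 2022.

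**Step 3: implied end of accrual.** 30 November 2022 − 8 months = 30 March 2022. From 1 October 2021 that is 180 days.

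**Step 4: participants with data on a given date.** For visit month m and calendar date t,

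n(t) = 120 × (days from 1 October 2021 to t − m months) / 180, held between 0 and 120.

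| Date (2022) | 8-month data | 4-month data |
|---|---|---|
| 1 June | 120 × 0/180 = 0 | 120 × 123/180 = 82 |
| 30 June | 120 × 29/180 = 19.3 (16%) | 120 × 150/180 = 100 |
| 31 August | 120 × 91/180 = 60.7 | 120 |
| 31 October | 120 × 150/180 = 100 | 120 |
| 30 November | 120 | 120 |

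So between 120 (1 June) and about 101 (30 June; 120 − 19.3 = 100.7) primary-endpoint assessments would be outstanding when interviews open.

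**Step 5: a scenario not used.** Protocol 5.4 speaks of recruiting over 10 months. From 1 October 2021, 10 + 8 months leads to 1 April 2023, which contradicts the November 2022 end of follow-up. It is left out; it would only lengthen the overlap.

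**Step 6: put the statements together.**
1. The moderator review comes before the interviews (Synopsis, Section 4).
2. It needs outcomes by arm (7.2.1).
3. Interviews start by June 2022 (4.1).
4. Analysis starts in December 2022, after follow-up ends (4.1, 9.6).

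Statements 1 to 3 imply a by-arm analysis by June 2022, and statement 4 places all analysis later. They cannot all stand as written. This does not depend on the accrual assumption, which sets only how much data an early review would have.

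The stakeholder sessions need a separate, conditional argument. They carry no date. If the 30 November 2022 limit on data collection covers Aim 3, they too fall before the analysis. If it covers only the RCT, they need not.

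**The case against.** **The calendar is looser than it looks.** Only a start date is given for the interviews. There is no end date, and the stakeholder sessions are undated. This stands: one cannot say that every interview precedes the analysis. It does not touch the moderator step, which is placed ahead of the first interviews.

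**The preliminary findings may be harmless.** Non-comparative material exists: the 10-person comprehension test, the small in-person pilot in China, session completion and coded written responses. Section 4 says that these stakeholders could implement the intervention if it proves efficacious, which fits efficacy not yet being known. The interview guide is held outside these documents. This stands too: a reader might infer that stakeholders are to be shown results by arm, but the text does not say so. It merely fails to exclude it.

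**The review could use 4-month data.** About 82 of 120 would be available on 1 June, and the SAP specifies moderation at 4 months. That answers the charge that only a sliver of data exists. It does not resolve the conflict, because 4-month outcomes by arm would still be opened before December, with 8-month follow-up running.

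**The harm is indirect.** Participants complete the surveys online and already know their arm. With the last randomization on 30 March 2022, the 17-week treatment window closes on about 27 July 2022. No text says that the stakeholders interviewed have contact with trial participants. This is fair, and it limits the claim to a plausible risk.

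**This is a preliminary-efficacy trial with no stopping rule tied to such a look.** Agreed. A reader might infer an inflated type I error, but no test, boundary or decision is attached to the review, so none is shown.

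**Conclusion.** The order of steps in the Synopsis and Section 4 conflicts with the calendar in Section 4.1. Both can be followed only by analysing outcomes by arm during follow-up, about six months before the stated analysis start. Under uniform accrual from 1 October 2021 to 30 March 2022 and no dropout, such a review in June 2022 would have 8-month data on 0 to 19 of 120 participants, and 4-month data on about 82 to 100.

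The stakeholder part is weaker. The findings to be shown are undefined, the sessions are undated, and their place before the analysis depends on Section 9.6 covering Aim 3. What can be said is that no rule keeps by-arm results out of them.

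An effect on self-reported outcomes or retention is plausible but not demonstrated. Because the SAP summary was revised on 24 January 2023 and leaves the outcome distribution and covariate adjustment open, a reader might also infer that early results shaped those choices. The documents give no evidence of that, or that an early review took place. The point merits a protocol change because a short, specific rule removes the risk.

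**What to change.** Amend the Aim 3 text in the Synopsis, Section 4 and Section 6.1 together:

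1. State that no outcome or moderator results by arm are produced for Aim 3, or shown in it, until the last 8-month survey has been received.
2. Limit the review before the interviews to completion metrics (sessions completed, points of drop-off), and move the moderator review to the December 2022 to May 2023 analysis period. This is needed whichever option is taken in item 3.
3. Either define the preliminary findings as non-comparative material (comprehension test, acceptability, completion), or hold the stakeholder sessions after follow-up closes and extend the Section 9.6 data-collection date for Aim 3 only.

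If interviews or sessions have already been held, record what was reviewed or shown, to whom and when.

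The cost is about one paragraph of protocol text, repeated where the Aim 3 steps appear. Participant interviews can still start in June 2022. Stakeholder sessions are delayed by up to about six months, or run without efficacy results. No extra participants or staff are needed.
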